3. STUDY PLAN AND PROCEDURES

3.1 Overall study design and flow chart

This is an 8 week, randomised, double blind, double dummy, national, multicentre study with 3 parallel treatment groups: rosuvastatin 10 mg, rosuvastatin 20 mg and placebo. The primary end point of the study is the change in triglycerides levels from baseline to week 8. Approximately 10 to 12 centres will be required in order to recruit 330 randomised patients, of whom 285 to 300 are expected to be fully evaluable (i.e., to allow for approximately 10 to 15% of randomised patients being non-evaluable). The approximate numbers of randomised patients will be recruited from Mexico City (150 patients), Monterrey (90 patients), Guadalajara (60 patients), Toluca (30 patients) and San Luis Potosi (30 patients). It is anticipated that in order to achieve this number of randomised patients, approximately 990 patients will need to enter the lead-in period of the study (screen failure rate 3:1). Centres will be required to randomise approximately 30 patients each. Centres may be discontinued from the study if recruitment rates are poor and new centres may be added if necessary to achieve recruitment goals. Recruitment will be competitive across cities and centres (thus, centres numbers are approximate). There is no maximum number of patients that centres can recruit. and centres will stop enrolment once enough patients are screened to provide the projected number randomised.

There are 4 clinic visits planned. Visit 1 and 2 occurs during the lead-in period. Visit 2.1 is the randomisation visit, and Visit 3 occurs during the randomised treatment period, is the final visit. For visit 1, the allowed window will be ± 3 days, for visit 2 the allowed visit window will be ± 3 days. For visit 2.1 the allowed visit window will be ± 2 day and for visit 3 the allowed visit window will be ± 3 days.

Male and female patients aged ≥ 18 with hypertriglyceridemia (HTG) and statin naïve (as defined by protocol) will be recruited. Patients will then enter a 4-week lead-in period during which they will undergo TLC dietary advice (see Appendix F) and no lipid lowering therapy will be allowed. All eligible patients will be randomised in a 1:1:1 ratio to receive ether rosuvastatin 10 or 20 mg/day or placebo once a day. Patients will be followed for 8 weeks. All patients will be offered the opportunity to continue with active commercially available therapy with rosuvastatin once the protocol is complete.

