6.2 Description of outcome variables in relation to objectives and hypotheses

Each outcome variable relates to the corresponding objective as described in Section 4.7.

Primary efficacy outcome variable

1. Percentage change in TG levels from baseline to week 8.

Secondary efficacy outcome variables

- 1. Percentage change in non-HDL-C levels from baseline to week 8.
- 2. Percentage change in lipids and lipoproteins (different to TG and non-HDL-C) from baseline to week 8 (LDL-C, TC, HDL-C, ApoA1, ApoB, TC/HDL-C; LDL-C/HDL-C; nonHDL-C/HDL-C and ApoB/ApoA1 indexes).
- 3. Percent change of hsCRP from baseline to week 8.

Secondary safety outcome variables

1. Safety evaluation as determined by the incidence and severity of adverse events and abnormal laboratory values

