6.5 Determination of sample size

The primary outcome variable for this study, which the sample size calculation has been based on, is the change in TG levels from baseline to Week 8.

Hypothesis testing will be undertaken to assess whether this change from baseline in TG levels is significantly different from zero (i.e., testing for a positive effect compared to baseline) for each of the rosuvastatin 10 mg and rosuvastatin 20 mg treatment groups. Similar hypothesis testing will also be performed for the placebo group.

No adjustment will be applied for the two rosuvastatin groups since the hypothesis testing in each of the treatment groups is independent. Therefore a 2-sided significance level of 5% will be applied for testing for a positive effect versus baseline. The required power is 90%.

Data taken from the literature suggest that an intervention with RSV will reduce TG levels between 22 and 25% average, with a maximum of 37% from baseline (expected p for sample 1(placebo):0.029; expected p for sample 2(RSV):0.229). We need a minimum of 67 fully evaluable patients per treatment arm to reach the 2-sided alpha 0.050 with a potency of 90% and a confident interval of 95%. Increasing sample size to 100 per arm increases potency to 97%.

As there are about 10 to15% patients that would probably not complete the 8 weeks treatment period (non-evaluable patients), we will increase the patients per treatment arm to 110 (a total of 330 randomised patients). As we have the facility of doing the trial in at least 10 centers, we can easily reach the target patients per treatment arm. Assuming a screen failure rate of 3:1 we will require approximately 990 patients to enter the study.

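### Section 6.5 sizes the trial as a comparison of two proportions, so its 90% and 97% power do not belong to the continuous TG endpoint or to any planned test

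*Protocol*

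**What the plan says.** Section 6.2 defines the primary efficacy variable as "Percentage change in TG levels from baseline to week 8", and Table 5 in Section 4.7 agrees. Section 6.5 says the calculation is based on the change in TG to week 8. It describes testing that change against zero within each arm, and sets alpha on that footing: "Therefore a 2-sided significance level of 5% will be applied for testing for a positive effect versus baseline". It adds: "The required power is 90" per cent.

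The effect assumption is that "an intervention with RSV will reduce TG levels between 22 and 25% average, with a maximum of 37% from baseline", followed at once in parentheses by "expected p for sample 1(placebo):0.029; expected p for sample 2(RSV):0.229". The result is: "We need a minimum of 67 fully evaluable patients per treatment arm to reach the 2-sided alpha 0.050 with a potency of 90" per cent. Section 6.5 then gives 97% power at 100 per arm and randomises 110 per arm (330 in all) to allow for 10 to 15% non-evaluable patients.

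On the tests themselves, Section 6.3 speaks of superiority versus baseline. Section 6.4.1.1 lists a Friedman analysis and Mann-Whitney tests of each rosuvastatin arm against placebo. Only the synopsis adds a within-group Wilcoxon test.

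**The concern.** The inputs are two probabilities, one per arm, while the endpoint is a continuous percentage change analysed by ranks. Power for a continuous endpoint depends on its SD, and Section 6.5 gives none. A two-proportion formula takes the variance as p(1−p), which has no connection with how much percentage TG change varies between patients.

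The section also disagrees with itself about the test being sized. The text describes one-sample tests against zero; the inputs describe placebo against rosuvastatin. At stake is the only power statement for the primary endpoint of a placebo-controlled trial, which as written cannot be checked against the analysis that will be done. This is not detail left to the SAP, because the protocol makes the calculation and states the power.

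**Working it through.** **1. Reproduce the stated 67.** Inputs from Section 6.5: p1 = 0.029, p2 = 0.229, difference 0.200, two-sided alpha 0.05 (z = 1.960), power 90% (z = 1.2816). The mean proportion is 0.129.

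- √(2 × 0.129 × 0.871) = 0.4740
- √(0.029 × 0.971 + 0.229 × 0.771) = √0.20472 = 0.4525
- Uncorrected n = (1.960 × 0.4740 + 1.2816 × 0.4525)² / 0.200² = 2.277 / 0.04 = 56.9
- Continuity-corrected n = (56.9 / 4) × [1 + √(1 + 4 / (56.9 × 0.2))]² = 66.5, so **67 per arm**

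The match is exact. Other two-sided variants give 57 (uncorrected), 54 (unpooled) and 49 (arcsine). Corrected power is 90.2% at 67 and 98.4% at 100, the latter close to the stated 97%.

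**2. What that formula assumes.** It fixes the patient-level SD at √(p(1−p)): √0.0282 = 0.168 for placebo and √0.1766 = 0.420 for rosuvastatin. These follow from the inputs alone and are not measurements of TG variability.

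**3. What the figures would need for the real endpoint.** With a 20-point difference and a normal approximation for two means, 90% at 67 per arm requires SD = 20 / [(1.960 + 1.2816) × √(2/67)] = 35.7 points (34.9 for Mann-Whitney at efficiency 0.955). The 97% at 100 per arm requires 36.8. The protocol states no such value.

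**4. Power at the numbers expected.** 110 × 0.85 = 93.5 and 110 × 0.90 = 99, so about 94 to 99 evaluable per arm. For Mann-Whitney I scale n by 0.955 (its efficiency under normality) and use the noncentral t with noncentrality 20 / [SD × √(2 / (0.955n))]. For the within-arm test of a 22.9% fall I use noncentrality 22.9 × √(0.955n) / SD. Every SD is an assumption.

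| Assumed SD (points) | Mann-Whitney, n = 94 | Mann-Whitney, n = 99 | Within-arm, n = 94 | Within-arm, n = 99 |
|---|---|---|---|---|
| 35 | 96.8% | 97.4% | >99.9% | >99.9% |
| 40 | 91.5% | 92.8% | >99.9% | >99.9% |
| 45 | 84.2% | 86.0% | 99.7% | 99.8% |
| 50 | 76.0% | 78.1% | 99.0% | 99.3% |
| 60 | 60.3% | 62.6% | 94.7% | 95.7% |

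Between arms, power falls below 90% once the SD exceeds about 41 (n = 94) to 42 (n = 99). Which test is primary therefore matters far more than the choice between 94 and 99 patients.

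**The case against.** Section 6.5 labels its inputs only as expected p and never says they are mean reductions. That reading is an inference: they directly follow the 22 to 25% average, 0.229 lies within that range, and no responder threshold exists. The point stands. But if they were responder rates, they would belong to an endpoint and a test that this trial does not have, so the mismatch survives either reading.

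A reader might infer that the trial is underpowered. The protocol does not support that. The low figures come only from the between-arm test at assumed SDs above about 42. For the versus-baseline test named in Sections 6.3 and 6.5, power is about 95% or more throughout the range shown.

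A reader might also count related figures as errors. Section 3.1 has 330 randomised, "of whom 285 to 300 are expected to be fully evaluable", whereas 10 to 15% loss gives 280 to 297; and the city targets sum to 150 + 90 + 60 + 30 + 30 = 360. Section 3.1 calls the loss rate and the city numbers approximate and recruitment competitive, and 12 centres of about 30 also make 360. These are editorial. Likewise, falling short of 100 evaluable per arm changes nothing on the sponsor's own method: corrected power at 94 to 99 is 97.7% to 98.3%.

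**Conclusion.** Section 6.5 is wrong as written. Its 67 per arm is correct arithmetic for a comparison of two proportions that this trial does not make, and the stated 90% and 97% power attach to neither the continuous TG endpoint nor any planned test. The section also leaves unclear whether the sizing serves the test against baseline or the comparison with placebo.

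The true power cannot be derived from the protocol. Between arms it runs from about 97% (SD 35) to 76–78% (SD 50) at 94 to 99 evaluable per arm, given a 20-point difference, approximate normality and the assumed SDs. Within arm it is about 95% or more up to SD 60. The defect lies in the justification; the sample size of 330 is not shown to be inadequate.

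**What to change.** Keep 330 patients and rewrite Section 6.5 in this order:

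1. Reconcile which comparison is primary: versus baseline (Sections 6.3 and 6.5) or each dose versus placebo (Section 6.4.1.1). Align the synopsis with the answer.
2. Replace the two-proportion calculation with one for percentage change, or log ratio, in TG, using that test. State the assumed effect, the SD and its source, and the alpha. The present reason for 5% per arm is written for within-arm tests and must be restated if the placebo comparison is chosen.
3. In place of the 90% and 97% claims, report power at about 94 to 99 evaluable per arm over a range of SDs.

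The evaluable range and city totals in Section 3.1 can be tidied in the same edit.

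The cost is one rewritten section plus the decision on the primary comparison. Enrolment is unchanged. The restated power may look less favourable if the sourced SD is large.

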7. STUDY MANAGEMENT

7.1 Monitoring

Before first patient into the study, a representative of AstraZeneca will visit the investigational study site to:

- Determine the adequacy of the facilities
- Discuss with the investigator(s) (and other personnel involved with the study) their responsibilities with regard to protocol adherence, and the responsibilities of AstraZeneca or its representatives. This will be documented in a Clinical Study Agreement between AstraZeneca and the investigator

During the study, a monitor from AstraZeneca or company representing AstraZeneca will have regular contacts with the study site, including visits to:

• Provide information and support to the investigator(s)

- Confirm that facilities remain acceptable
- Confirm that the investigational team is adhering to the protocol, that data are being accurately recorded in the CRFs, and that investigational product accountability checks are being performed
- Perform source data verification (a comparison of the data in the CRFs with the patient's medical records at the hospital or practice, and other records relevant to the study). This will require direct access to all original records for each patient (e.g., clinic charts).

The monitor or another AstraZeneca representative will be available between visits if the investigator(s) or other staff at the centre need information and advice.

7.2 Audits and inspections

Authorised representatives of AstraZeneca, a regulatory authority, an Independent Ethics Committee (IEC) or an Institutional Review Board (IRB) may visit the centre to perform audits or inspections, including source data verification. The purpose of an AstraZeneca audit or inspection is to systematically and independently examine all study-related activities and documents to determine whether these activities were conducted, and data were recorded, analysed, and accurately reported according to the protocol, Good Clinical Practice (GCP), guidelines of the International Conference on Harmonisation (ICH), and any applicable regulatory requirements. The investigator should contact AstraZeneca immediately if contacted by a regulatory agency about an inspection at his or her centre.

7.3 Training of staff

The principal investigator will maintain a record of all individuals involved in the study (medical, nursing and other staff). He or she will ensure that appropriate training relevant to the study is given to all of these staff, and that any new information of relevance to the performance of this study is forwarded to the staff involved.

7.4 Changes to the protocol

Study procedures will not be changed without the mutual agreement of the Co-ordinating Investigator and AstraZeneca.

If it is necessary for the study protocol to be amended, the amendment or a new version of the study protocol (Amended Protocol) must be notified to or approved by each IRB or IEC, and also by the local regulatory authority, before implementation. Local requirements must be followed.

If a protocol amendment requires a change to a particular centre's Informed Consent Form, then AstraZeneca and the centre's IRB or IEC must be notified. Approval of the revised Informed Consent Form by AstraZeneca and by the IRB or IEC is required before the revised form is used.

AstraZeneca will distribute amendments and new versions of the protocol to each principal investigator(s), who in turn is responsible for the distribution of these documents to his or her IRB or IEC, and to the staff at his or her centre. The distribution of these documents to the regulatory authority will be handled according to local practice.

7.5 Study agreements

The principal investigator at each centre must comply with all the terms, conditions, and obligations of the Clinical Study Agreement for this study. In the event of any inconsistency between this Clinical Study Protocol and the Clinical Study Agreement, the Clinical Study Protocol shall prevail.

7.6 Study timetable and end of study

Before a patient's enrolment in the study and any study-related procedures are undertaken the following should be fulfilled:

- Signed Clinical Study Protocol and other agreements between AstraZeneca and the Principal Investigator/Study Site.
- Approval of the study by the IRB/IEC
- Approval of the study by the regulatory authority.

The timetable for the study is as follows:

Estimated date of first patient enrolled	May 2007
Estimated date of last patient enrolled	October 2007
Estimated date of last patient completed	February 2008
Estimated recruitment period	6 months

Date of last patient completed is defined as the date of the last visit of the last patient

8. ETHICS

8.1 Ethics review

The final study protocol, including the final version of the Informed Consent Form, must be approved or given a favourable opinion in writing by an IRB or IEC as appropriate. The investigator must submit written approval to AstraZeneca before he or she can enrol any patient into the study.

The principal investigator is responsible for informing the IRB or IEC of any amendment to the protocol in accordance with local requirements. In addition, the IRB or IEC must approve

all advertising used to recruit patients for the study. The protocol must be re-approved by the IRB or IEC annually, as local regulations require.

AstraZeneca will provide IECs and the principal investigators with safety updates/reports according to local requirements.

The principal investigator is also responsible for providing the IRB with reports of any serious and unexpected adverse drug reactions from any other study conducted with the investigational product. AstraZeneca will provide this information to the principal investigator.

Progress reports and notifications of serious and unexpected adverse drug reactions will be provided to the IRB or IEC according to local regulations and guidelines.

8.2 Ethical conduct of the study

The study will be performed in accordance with ethical principles that have their origin in the Declaration of Helsinki and are consistent with ICH/Good Clinical Practice, applicable regulatory requirements and the AstraZeneca policy on Bioethics.

8.3 Informed consent

The principal investigator(s) at each centre will ensure that the patient is given full and adequate oral and written information about the nature, purpose, possible risk and benefit of the study. Patients must also be notified that they are free to discontinue from the study at any time. The patient should be given the opportunity to ask questions and allowed time to consider the information provided.

The patient's signed and dated informed consent must be obtained *before* conducting any procedure specifically for the study, including the following:

• Asking the patient to attend the clinic fasted at the first visit.

The principal investigator(s) must store the original, signed Informed Consent Form. A copy of the signed Informed Consent Form must be given to the patient.

If modifications are made according to local requirements, the new version has to be approved by AstraZeneca.

8.4 Patient data protection

The Master Informed Consent Form will incorporate wording that complies with relevant data protection and privacy legislation. Pursuant to this wording, patients will authorise the collection, use and disclosure of their study data by the investigator and by those persons who need that information for the purposes of the study.

The Master Informed Consent Form will explain that study data will be stored in a computer database, maintaining confidentiality in accordance with national data legislation. All data

computer processed by AstraZeneca will be identified by patient initials, e-code and study code.

The Master Informed Consent Form will also explain that for data verification purposes, authorised representatives of AstraZeneca, a regulatory authority, an IRB or IEC may require direct access to parts of the hospital or practice records relevant to the study, including patients' medical history.

An overdose without associated symptoms should not be recorded as an AE in the CRFs. The overdose should be reported on the separate AZ "Clinical Study Overdose Report Form".

9.4 **Procedures in case of pregnancy**

Women who are pregnant, planning a pregnancy or not using reliable mechanical or chemical contraception are not permitted to enter this study.

If a patient becomes pregnant during the study they will be discontinued from the study.

Pregnancy itself is not regarded as an adverse event unless there is a suspicion that the investigational product under study may have interfered with the effectiveness of a contraceptive medication.

The outcome of all pregnancies (spontaneous miscarriage, elective termination, normal birth or congenital abnormality) must be followed-up and documented even if the patient was discontinued from the study. All reports of congenital abnormalities/birth defects are SAEs. Spontaneous miscarriages should also be reported and handled as SAEs.

All outcomes of pregnancy must be reported to AstraZeneca on the pregnancy outcomes report form. The first part of the form is used to collect information before the outcome of the pregnancy is known. The form should be completed as soon as possible after it has been identified that the patient received study drug during pregnancy and should be reported to the appropriate AstraZeneca Drug Safety Department within 45 days. The second part of the form records the outcome of the pregnancy and should be sent to the appropriate AstraZeneca Drug

Safety Department within AE or SAE timeframes, or within 45 days if the outcome of pregnancy is a normal birth.

